## STUDY ENDPOINTS AND COVARIATES

**Table 1: Primary and Secondary Efficacy Endpoints**

Primary Clinical Efficacy Variables:	The primary clinical efficacy variable is time to intubation event in hours from the start of study infusion.
Secondary Clinical Efficacy Variables:	

1. All-cause hospital mortality

2. The requirement for intubation and invasive mechanical ventilation

3. Length of non-invasive mechanical ventilation in hours

4. Length of oxygen therapy in hours

5. Length of ICU stay in hours

6. Length of hospital stay in hours

7. Difference in proportion of patients intubated

8. Difference in proportion of patients intubated and on MV

Secondary Biochemical Efficacy Variables:	

1. Plasma levels of citrulline at 2 hours, 12 hours, and study days 2, 4, 8, 10.

2. Plasma levels of arginine at 2 hours, 12 hours, and study days 2, 4, 8, 10.

3. Plasma NOx levels at 2 hours, 12 hours, and study days 2, 4, 8, 10.

**Table 2: Secondary Safety Endpoints**

Safety Variables:	

1. Primary safety variable is hemodynamic status, specifically worst vasopressor dependency index through day 10.

2. Incidence of reported adverse events.

Safety Evaluations:	
In addition to vasopressor dependency index, the following laboratory values will be used for safety assessment at baseline and daily through study day 4 when available.
 

1. Complete blood count with platelets

2. Basic Metabolic profile, including renal function

3. Liver function tests, including SGOT, SGPT, total bilirubin, and alkaline phosphatase

 
Adverse events will be recorded prospectively, including incidences of hypotension, hepatitis (i.e., the elevation of liver enzymes), and injection site reactions.

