Treatment Arms:	
 1. Patients will be randomized to IV Citrulline or placebo 2. Patients will receive an initial bolus of 20 mg/kg (maximum 1500 mg), followed by study infusion of 9 mg/kg per hour (maximum 700mg) for up to 10 days. 3. Patients, healthcare providers, and the sponsor will be blinded to which treatment the patient is receiving. The investigational pharmacy independent pharmacist will be unblinded to the treatment assignment and will deliver the correct infusion to the patient's bedside. 4. The time of initiation of the study drug infusion (either L-Citrulline or placebo will represent time zero. 5. Intravenous Citrulline: Patients randomized the citrulline arm will receive an initial loading bolus of 20 mg/kg (maximum 1500 mg) followed by an infusion of 9 mg/kg per hour (maximum 700 mg) for

	
a maximum of 10 days. The citrulline solution will be prepared as a 5% (50 mg/mL) isotonic solution in 5% dextrose water.
 
6. Placebo: Patients randomized to placebo will receive equal volume bolus and study infusion of 5% dextrose water for a maximum of 10 days.

Sample Size/Statistical Considerations:	
 1. The study will enroll up to 66 patients in a 1:1 ratio. 2. Patients will be analyzed on an intention to treat basis. 3. The primary outcome will be time to intubation event—from the initiation of the treatment until intubation for invasive mechanical ventilation—and will be compared using a log-rank test. 4. Plasma citrulline, arginine, and nitric oxide levels will be measured at 2 and 12 hours post-bolus and on days 2, 4, 6, 8, and 10 and compared using Linear mixed model or repeated measures ANOVA analysis. 5. The vasopressor dependency index (VDI) will be measured for hemodynamics. Worst vasopressor dependency index score over the first 6 days will be compared using ANCOVA analysis with the baseline index as the covariate. 6. SaO₂/FiO₂ or PaO₂/FiO₂ ratio will be utilized to measure the progression of ALI. Worst values from days 0, 2, 4, or 6, 8, or 10 will be compared between groups using repeated measures ANCOVA with the baseline value as the covariate.
Inclusion Criteria:	
 1. Age 18-65 years inclusive. 2. Clinical and laboratory evidence of COVID-19 (SARS-CoV2) infection with an acute hypoxic respiratory illness requiring hospitalization and oxygen therapy. 3. Admitted and transferred to floor without intubation.

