5.1.2 Study Assessments

The assessment of efficacy will include collection of plasma for analysis of citrulline and arginine levels at day 1 hours 0, 2, 12, and the alternating morning of study days the infusion is running for a maximum of 10 days, i.e., on days 2, 4, 6, 8 and 10. A patient will exit the study early if they have been weaned off all oxygen support before 10 days. Additional efficacy measures will include clinical outcomes, including progression of acute lung injury and lengths of hospital and ICU stay.

The assessment of safety will include collection of hemodynamic measurements at least every 4 hours on a hospital unit and--if a patient is critically ill in an ICU--hourly while the study material is infusing and for 12 hours after completion of the infusion in each patient. Hemodynamic measurements will be converted to a vasopressor dependency index for analysis if a patient becomes critically ill. Adverse event reporting will also serve as a means of safety analysis. Additional safety measures will be biochemical and hematologic laboratory measurements. The biochemical laboratory measurements, including liver function tests (ALT, AST, bilirubin, alkaline phosphatase), kidney function tests, and electrolytes, along with hematologic laboratory measurements, including complete blood count and platelet count, will be collected when available for any study day in order to evaluate for adverse events.

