APPENDIX A: Schedule of Events

Measurement	Day 0 (baseline)	Day 1	Day 2	Day 3	Day 4	Day 5	Day 6	Day 7	Day 8	Day 9	Day 10	Day 11	Day 12-DC	Day 28 ^e Follow-up	Day 60 ^e Follow-up
Informed Consent	X														
Demographics- Hx & Px	X														
Eligibility Assessment	X														
Pregnancy Test	Xc														
Study Drug Administration		X	X	X	X	X	X	X	X	X					
Vital Signs		X	X	X	X	X	X	X	X	X	X	X	X		
Mean Arterial Pressure		Xa,b,d	X	X	X	X	X	X	X	X	X	X			
Vasopressor Dosages		Xa,b,d	X	X	X	X	X	X	X	X	X	X			
Basic Metabolic Panel		A	A	A	A	A	A	A	A	A	A	A			
CBC		A	A	A	A	A	A	A	A	A	A	A			
LFTs		Ab	A	A	A	A	A	A	A	A	A	A			
D-dimer blood draw		Xa,b	X		X		X		X		X		X		
CRP		Xa,b	X		X		X		X		X		X		
5 ml blood for citrulline etc.		Xa,b	X		X		X		X		X				
SaO2/ FiO2 ratio		X	X	X	X	X	X	X	X	X	X	X			
PaO2		X	X	X	X	X	X	X	X	X	X	X			
ABG		A	A	A	A	A	A	A	A	A	A	A			
Hospital status		X	X	X	X	X	X	X	X	X	X	X	X	X	X
ICU status		X	X	X	X	X	X	X	X	X	X	X	X	X	X
Non-invasive ventilation status		X	X	X	X	X	X	X	X	X	X	X			
Invasive ventilation status		X	X	X	X	X	X	X	X	X	X	X			
ConMed Review		X	X	X	X	X	X	X	X	X	X	X	X	X	X

Adverse Event Review		X	X	X	X	X	X	X	X	X	X	X	X	X	X	X
----------------------	--	---	---	---	---	---	---	---	---	---	---	---	---	---	---	---

a= measurement should be recorded or performed at hours 0, 2 and 12

b= Day 1 hour 0 samples/procedure must be collected/recorded before study drug is administered.

c= only perform if patient is of childbearing potential

d= must be collected 15 minutes prior to administration of study medication

e= Day 28 and Day 60 are telephone follow ups

X= Study Procedure A= Standard of Care

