## **STUDY DESIGN**

This is a randomized, double-blind, placebo-controlled, phase II study to evaluate the safety and efficacy of intravenous L-Citrulline in reducing the length of time from the start of study infusion to an intubation event in hospitalized acutely ill patients with an acute hypoxic respiratory illness due to COVID-19 infection (SARS-CoV2). Patients age of 18 years old and less than 65 years old inclusive with COVID-19 infection (SARS-CoV2) will be included in the study.

Only subjects hospitalized at UAMS and requiring oxygen for an acute hypoxic respiratory illness due to COVID-19 (SARS-CoV2) will be included in this study. Study drug administration will occur exclusively in the hospital.

In addition, subjects will receive standard supportive care for acute hypoxic respiratory illness and failure.

Approximately 60 participants ages 18 years to 65 years, inclusive, who meet all the inclusion criteria and none of the exclusion criteria will be randomized into the study over approximately 6-9 months.

The study consists of an initial Study Drug bolus followed by a continuous infusion for a maximum of 10 days. The safety and efficacy will be evaluated through hemodynamic monitoring, laboratory assessment, oxygenation status, and biomarker measurements through study day 10. Adverse events will be monitored through study day 10. Clinical outcomes, including all-cause mortality, ICU length of stay, and hospital length of stay will be assessed through hospital discharge.

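### The laboratory safety assessment stops at study day 4, in conflict with a 10-day infusion and the plan's own later laboratory windows, so later bilirubin, creatinine and platelet changes have no planned comparison by arm

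*SAP*

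**What the plan says.** **Laboratory window.** SAP Table 2, under Safety Evaluations, lists the blood count with platelets, the metabolic profile with renal function, and the liver tests. It says they "will be used for safety assessment at baseline and daily through study day 4 when available". Protocol 2.0 (Study Summary, Safety Evaluations) is worded identically.

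**Exposure and other laboratory windows.**
- SAP Study Design: "The study consists of an initial Study Drug bolus followed by a continuous infusion for a maximum of 10 days". It continues: "The safety and efficacy will be evaluated through hemodynamic monitoring, laboratory assessment, oxygenation status, and biomarker measurements through study day 10". Protocol 5.1 agrees.
- Protocol 5.1.2 says that laboratory measurements "will be collected when available for any study day in order to evaluate for adverse events". SAP Study Assessments says the same.
- Protocol Appendix A marks the row "Basic Metabolic Panel" and the rows for blood count and liver tests on each of days 1 to 11. The entries are A, under the key "X= Study Procedure A= Standard of Care".

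**Adverse events.** Protocol 9.1 and 9.2 have liver enzyme elevation collected systematically, and 9.1 counts it as an adverse event. Protocol 9.3 lists outcomes of progressing COVID-19 illness that are not counted as adverse events. They include hepatic injury, raised bilirubin, renal failure, dialysis, raised creatinine and thrombocytopenia.

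**VDI.** The statistics row of the protocol synopsis says: "Worst vasopressor dependency index score over the first 6 days will be compared using ANCOVA analysis with the baseline index as the covariate". Elsewhere the synopsis gives day 10 (Study Design item 3 and the primary safety variable), and so does the SAP (Table 2 and Secondary Safety Endpoints). Protocol 10.5 uses any time after the start of infusion.

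**The concern.** Table 2 is the only place in the SAP that says which laboratory values enter the safety assessment and for how long. The methods under Secondary Safety Endpoints cover only VDI and adverse events. A programmer who follows the SAP would therefore reasonably stop at day 4, although patients may be infused for another 6 days. Neither document gives a reason for day 4.

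What is at stake is the check that does not depend on clinical judgement. Adverse event reporting relies on an investigator deciding that a change is clinically significant and not part of the illness. A summary of laboratory values by arm does not. It matters most for the values that Protocol 9.3 takes out of adverse event reporting, in the patients with the longest exposure.

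**Working it through.** The plan states no figure to reproduce. The check is a count of days and a comparison of capture routes.

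**1. Days outside the window**

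Inputs: last day of the laboratory window = 4 (SAP Table 2, protocol synopsis); maximum infusion = 10 days (SAP Study Design); scheduled laboratory days = 1 to 11 (Appendix A).

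- Infusion days after day 4: 10 − 4 = 6, and 6/10 = 60%. Nominally 240 − 96 = 144 of 240 hours.
- Scheduled laboratory days after day 4: 11 − 4 = 7, and 7/11 = 64%.
- Covered now: 4/10 infusion days and 4/11 laboratory days (36%).
- Covered if the window runs through day 10, with day 11 added: 10/10 and 11/11.

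These are calendar days, not measurements.

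**2. Which changes after day 4 still have a route into the analysis**

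| Change first seen after day 4 | Laboratory assessment (Table 2) | Adverse event table |
|---|---|---|
| Liver enzymes | No | Yes (Protocol 9.1, 9.2) |
| Bilirubin | No | Not counted (9.3) |
| Creatinine, renal failure | No | Not counted (9.3) |
| Platelets | No | Not counted (9.3) |

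The first row takes 9.1 and 9.2 as governing enzymes. The hepatic injury entry in 9.3 sits awkwardly beside them.

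**3. What a late summary could show (illustration, assumed rates)**

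If a fraction p of the patients sampled in an arm has an abnormality that first arises after day 4, the chance of seeing at least one among n patients is 1 − (1 − p)^n. The documents give no p, so take 5% to 10%.

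| n per arm | p = 5% | p = 10% |
|---|---|---|
| 30 | 1 − 0.95^30 = 0.785 | 1 − 0.90^30 = 0.958 |
| 33 | 1 − 0.95^33 = 0.816 | 1 − 0.90^33 = 0.969 |

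This assumes that every patient is still infused and sampled. If only half of 30 were (n = 15), the values would be 1 − 0.95^15 = 0.537 and 1 − 0.90^15 = 0.794. Under any of these assumptions, a summary cut at day 4 shows none of them.

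**4. VDI**

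A 6-day window would leave out 10 − 6 = 4 of 10 infusion days (40%). The SAP does not use that window. Its day-10 definition covers all 10.

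**The case against.** A reader might infer that late toxicity goes unseen, or that most on-treatment laboratory data are thrown away. The documents support neither.

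- **Other routes exist.** Laboratory values from any study day feed adverse event evaluation, and Protocol 9.2 has any change evaluated with no day limit. Adverse events are collected routinely to day 10, and later if reported or observed (9.5). The SAP tabulates all of them by arm. The safety officer reviews laboratory data daily (11.4), and anything suspected to be related to study drug is to be reported (11.5). This stands, and it answers the point for liver enzymes. It only partly answers it for bilirubin, creatinine and platelets. Daily review and suspicion about a single patient under blinding are not a comparison between arms, and 9.3 removes these changes from the adverse event counts by default.
- **Calendar days are not data.** Patients stop infusion when weaned off oxygen, and the tests are standard of care, taken when available. The share of values that fall after day 4 is therefore unknown. Day 11 also follows the end of infusion. All of this stands, so the 60% and 64% must not be read as data lost.
- **No named analysis is being cut short.** The SAP gives no statistical method for laboratory values at any day. This is correct, and it adds to the gap.
- **The 6-day VDI line does not alter the analysis.** A reader might infer that the primary safety variable is truncated. It is not. The 6-day wording occurs once, in the protocol synopsis, against day 10 elsewhere in the synopsis and in the SAP. Protocol 10.2 leaves the detailed methods to the SAP.

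**Conclusion.** The concern holds as an internal contradiction with a limited consequence. The day-4 limit in SAP Table 2 and the protocol synopsis cannot be squared with the 10-day infusion, the SAP's own laboratory assessment through day 10, collection on any study day, or the Appendix A rows on days 1 to 11. Up to 6 of 10 infusion days and 7 of 11 scheduled laboratory days lie outside it.

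The substantive gap is bilirubin, creatinine and platelets after day 4. Apart from events reported individually on suspicion, they have no planned comparison by arm. This conclusion assumes that Table 2 and Protocol 9.3 are applied as written. The days counted are the maximum possible, and the number of values affected cannot be derived from the documents. The issue should be corrected before database lock. It does not show that late toxicity would be missed altogether. The VDI wording is editorial.

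**What to change.** 1. In SAP Table 2 and in Safety Evaluations in the protocol synopsis, replace the day-4 limit with all available values through study day 10. Add the day 11 values scheduled in Appendix A as a post-infusion check. Day 10 then matches the evaluation period in the SAP Study Design section and routine adverse event collection.
2. State the laboratory summary in the SAP: by treatment arm, for example the worst post-baseline value and the shift from baseline for each test, including bilirubin, creatinine and platelets. Show the number of patients with a value on each day by arm. Patients who recover leave the later days, and a worst value depends on how often a test was done.
3. In the statistics row of the protocol synopsis, change the VDI window from the first 6 days to through day 10. The SAP needs no change on this item.

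Cost: wording in the SAP and the protocol synopsis, and a small set of summary tables. No new blood draws are needed, since the tests are standard of care, but late values may be incomplete for the same reason. If the change is made before database lock, planned for September 2021, the window is set without sight of unblinded results.

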**Table 3: Covariates**

Independent Variables:	Age is likely to be an independent covariate and the intention is to assess its contribution in two age groups (younger and older) as per protocol.
Dependent Variables:	The outcome variable of interest being reduction in morbidity and mortality outcomes. A fuller list is as per the secondary endpoints above.
Continuous variable:	The study involves markers of respiratory function such as P/F ratios and hemodynamic markers such as VDI that are considered continuous variables and are expected to change with study treatment.

## **ANALYSIS POPULATIONS**

The intent-to-treat (ITT) population will be used for all efficacy and safety analyses. This will consist of all randomized patients irrespective of whether the patient received study drug or the patient's compliance with the study protocol, in the treatment group assigned by the randomization system.

## **SAFETY POPULATIONS**

The Safety population will include all subjects who take at least one dose of study drug during the study. For the safety analysis set, subjects are assigned to a treatment group based on the treatment actually received, regardless the treatment randomized.

## **DATA HANDLING AND ELECTRONIC TRANSFER OF DATA**

SAS data extracts will be transferred via sFTP (secure file transfer protocol) portal as per Medrio SOP on data transfer. Data files will be created as per the DMP (Data Management Plan).

## **ANALYSIS CONVENTIONS**

### **Statistical Significance**

Unless otherwise specified, statistical tests will be 2-sided for all analyses and the null hypothesis will be rejected at the significance level of  $\alpha = 0.05$ . P-values will be rounded to four decimal places before assessing statistical significance. In this Phase II study, no adjustment for multiple comparisons for the primary clinical, safety, and biochemical outcomes will be made. The multiplicity from testing secondary clinical, biochemical, and safety outcomes will be adjusted based on a Hochberg procedure (Sakamaki, 2013; Ye et al., 2012).

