10.2 General Statistical Approach

Before database lock, a statistical analysis plan (SAP) will be issued as a separate document, providing full detailed methods for the analyses outlined below. Multiplicity adjustment approach will be described as per industry guidance for multiple comparisons across all the endpoints to eliminate Type 1 errors. Sensitivity analysis will be applied to handle missing data and sources of uncertainty. The protocol study team may revise the plan during the study to accommodate clinical trial protocol amendments and to make changes to adapt to unexpected issues in study execution and data that affect planned analyses. The protocol team will conduct all statistical analyses following the statistical principles for clinical trials as specified in International Council on Harmonization Topic E9. Any deviations from the planned analyses

will be described and justified in the final integrated clinical study report. The protocol study team will present overall and treatment specific data and summary tables.

All statistical tests will be two-sided. All summary tables for quantitative measures will display means, standard deviations, median and range, as well as number of missing data (if relevant). All summary tables for categorical variables will display counts, percentages, and number of missing data (if relevant).

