10.5 Primary Endpoints

Time to an intubation event in hours from the start of the study drug infusion or overall duration of mechanical ventilation will represent the primary clinical endpoint. The number of patients starting intubation over time will be displayed in the form of survival curves using the Kaplan-Meier method and analyzed using a two-sided log-rank test. Statistical significance will be claimed if the computed p-value is equal to or less than 0.05.

Citrulline and arginine plasma levels will represent the primary biochemical endpoint of this study. A 5 mL sample of blood will be obtained for amino acid analysis at hour 0 before study medication is administered, 2 and 12 hours after the bolus and as close as possible to 8 AM on days 2, 4, 6, 8, and 10. Samples will be collected in citrated tubes and placed on ice until they can be centrifuged. Plasma and cellular components will be frozen at -70 °C until batch analysis. Concentrations of citrulline, arginine, and ornithine will be measured in the plasma samples using cation-exchange chromatography with a Beckman 7300 amino acid analyzer or equivalent. The analysis team will provide the means and standard

deviations for citrulline, arginine, and ornithine plasma levels separately for each treatment group. A generalized linear mixed model (GLMM) with appropriate link function (i.e., identity link for continuous outcome) will be used to compare these plasma amino levels across the two intervention groups. The model will examine how the treatment means differ (i.e., main treatment effect), how treatment means change over time (i.e., main time effect), and how differences between treatment means change over time (i.e., treatment-by-time effect).

The primary safety outcome will be worst VDI any time after start of infusion. VDI is a continuous variable calculated by dividing vasopressor index (summation of all pressors) by MAP. VDI will be calculated at baseline (immediately before start of the infusion), 2 hours after completion of the bolus, and every 4 hours during the infusion. Worst VDI will be compared between groups using ANCOVA analysis with the baseline VDI as the covariate.

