## Primary Endpoints

### Primary Clinical Endpoint

- The primary clinical efficacy variable is time to intubation event in hours from the start of study infusion.

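### Protocol 10.2 promises multiplicity control across all endpoints, but the SAP leaves primaries unadjusted and tests an ungated Hochberg family; with one primary, the chance of a false claim is about 6–10%

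*SAP*

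**What the plan says.** Protocol 10.2 (General Statistical Approach) leaves the detail to the SAP but states what it must achieve: "Multiplicity adjustment approach will be described as per industry guidance for multiple comparisons across all the endpoints to eliminate Type 1 errors".

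The SAP's only multiplicity text is under Analysis Conventions, Statistical Significance. It has three parts:

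- A default for every test: "statistical tests will be 2-sided for all analyses and the null hypothesis will be rejected at the significance level of" 0.05, unless otherwise specified.
- For primaries: "In this Phase II study, no adjustment for multiple comparisons for the primary clinical, safety, and biochemical outcomes will be made".
- For the rest: "The multiplicity from testing secondary clinical, biochemical, and safety outcomes will be adjusted based on a Hochberg procedure".

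The paragraph gives no other alpha for the Hochberg family, no condition on the primary result and no split of alpha. None appears in the SAP's sample size, primary, secondary, safety or interim sections either. Protocol 10.5 applies the full level to the primary clinical endpoint: "Statistical significance will be claimed if the computed p-value is equal to or less than 0.05".

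The number of primaries differs between places. Protocol 4.1 and 10.5 have a clinical, a biochemical and a safety primary; on the second, 10.5 says "Citrulline and arginine plasma levels will represent the primary biochemical endpoint of this study". The SAP's objectives and Primary Endpoints section list one: "The primary clinical efficacy variable is time to intubation event in hours from the start of study infusion". The SAP lists plasma levels and worst VDI as secondary, yet its Statistical Significance paragraph still speaks of three kinds of primary, and its Table 2 still labels VDI the primary safety variable.

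**The concern.** A Hochberg procedure controls the chance of a false rejection within the set of tests it is applied to. It says nothing about tests outside that set. The plan spends 0.05 on each unadjusted primary and, separately, 0.05 on the secondary family. The error across both is then above 0.05, even if time to intubation is the only primary.

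Nothing says what a Hochberg-adjusted secondary result means when time to intubation is not significant. A mortality, length-of-stay or biochemical finding could be reported as significant after adjustment, and a reader holding Protocol 10.2 would take it as protected across all endpoints. Mortality is a foreseeable case, since both documents give it its own power statement.

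**Working it through.** **The plan's own figures.** Neither document states a family-wise error rate. The stated design figures can be checked:

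- Log-rank power, hazard ratio 0.46 (3/6.5 = 0.4615), Freedman's formula with 60 events: Φ(√60 × (1 − 0.46)/(1 + 0.46) − 1.96) = Φ(2.865 − 1.960) = 81.7%, against 81% stated.
- Mortality 50% vs 17%, 30 per arm: 78.8%, against 80% stated.

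Both use the full two-sided 0.05.

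**Inputs for the error calculation**

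- Alpha 0.05, two-sided, for each primary and for the Hochberg family (SAP, Statistical Significance).
- Number of primaries: one (SAP objectives and Primary Clinical Endpoint) or three (the kinds named under Statistical Significance). Two is the case in which plasma citrulline is set aside as a true null.
- Number of secondary tests: the SAP lists 8 clinical, 4 biochemical and 2 safety items. Some overlap, and adverse events are only tabulated. Range used: 8 to 14.
- Correlation between test statistics: not in the documents. Assumed common value, varied from 0 to 0.9.

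**Independent tests.** With k separate 0.05 allocations the chance of at least one false claim is 1 − 0.95^k:

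- one primary plus the family: 1 − 0.95² = 9.75%
- two primaries plus the family: 1 − 0.95³ = 14.3%
- three primaries plus the family: 1 − 0.95⁴ = 18.5%

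**Correlated tests.** Simulation with 300,000 draws per scenario: all nulls true, equicorrelated normal statistics, primaries rejected at p ≤ 0.05, Hochberg at 0.05 on the secondaries, counting any rejection.

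| Correlation | One primary | Two primaries | Three primaries |
|---|---|---|---|
| 0 | 9.6% | 14.2% | 18.4–18.6% |
| 0.3 | 8.9% | 12.9–13.0% | 16.6–16.8% |
| 0.5 | 7.7–7.9% | 11.2–11.3% | 14.3–14.4% |
| 0.7 | 6.3–6.5% | 9.1–9.4% | 11.5% |
| 0.9 | 5.1–5.2% | 7.1% | 8.4% |

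At correlation 0.8 the figures are 5.7–5.8% for one primary and 10.0–10.1% for three.

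**Checks on the assumptions**

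- Unequal correlation (intubation endpoints 0.9, other clinical 0.3, biochemical 0.5): 8.2%, 12.2% and 16.1% for one, two and three primaries.
- One primary, with citrulline and arginine truly raised inside the secondary family: 9.6–9.7% at correlation 0, 8.9–9.0% at 0.3, 7.9–8.0% at 0.5.
- One primary, 30 per arm, log-rank for the primary and the planned Fisher tests for mortality and the intubation proportions, with assumed mortality 30%, intubation 30% or 86%, and correlation 0 to 0.8: about 7–8.5%.

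**With a gate.** If time to intubation is the sole primary and the family is tested only when it is significant, a false claim under the global null requires a false primary rejection. The overall error is then at most 5%, and primary power stays at 81.7%. If three unadjusted primaries were left standing, a gate would not be enough: 1 − 0.95³ = 14.3%.

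**The case against.** The strongest reply is that this is an open phase II choice. The SAP says what is and is not adjusted, ties this to the phase, and nowhere claims a 5% rate for the whole study. Within-family control of secondaries is a recognised approach, and the primary clinical test keeps its own 0.05. All of that stands. What it does not answer is Protocol 10.2, which commits the SAP to an approach across all endpoints. Either the scheme or the commitment has to change.

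A second reply is that the size is modest. Strong correlation and the conservatism of Fisher tests in 60 patients both pull it down; at correlation 0.9 with one primary it is about 5%. This also stands, and is why the result is given as a range. A uniformly high correlation is hard to support, however, for a family mixing mortality, length of stay, amino acids and VDI.

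Third, the SAP defines its Hochberg procedure partly by citation to two sources not available here, so its exact structure cannot be fully checked. A reader might infer separate families for the clinical, biochemical and safety domains, which would give 14.2% from the secondaries alone at correlation 0. The SAP refers to a single procedure, so that reading is not supported.

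**Conclusion.** The plan does not have the property Protocol 10.2 states. On the SAP's own endpoint list (one primary) and with all nulls true, the chance of at least one false claim is about 6–10% for correlations from 0.8 down to 0, and about 7–8.5% with the planned Fisher tests. Keeping the three kinds of primary named in the SAP's significance paragraph gives about 10–18%, or up to about 14% without the citrulline null. The correlations and the number of secondary tests are assumptions.

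Three stronger readings are tempting and not supported:

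- That the study's error rate is 18%. This needs three independent primaries, including a true null for plasma citrulline in patients infused with citrulline, whereas the SAP's endpoint list has one primary.
- That the primary test is compromised. Time to intubation, taken alone, is still tested at 0.05.
- That mortality is an unsized endpoint that could stand in for the only sized one. Protocol 10.4 and the SAP's sample size section power mortality separately.

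The issue is how claims beyond the primary are read, and the agreement between the two documents.

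**What to change.** 1. SAP, Statistical Significance: name time to intubation as the sole primary for error control, as the SAP's objectives and Primary Clinical Endpoint already do, and replace the statement that "no adjustment for multiple comparisons for the primary clinical, safety, and biochemical outcomes will be made". Leaving that statement in place would make a 5% claim untrue even with a gate.
2. State that the secondary efficacy outcomes, clinical and biochemical, form one Hochberg family, tested confirmatorily at two-sided 0.05 only if the stratified log-rank test is significant. Otherwise their p-values are nominal and exploratory.
3. Keep VDI and adverse events outside both the gate and the family. Report them with estimates, confidence intervals and nominal p-values whatever the efficacy result, so that a safety signal does not depend on an efficacy test.
4. Protocol 10.2: replace the aim of eliminating type 1 errors, which no procedure can do, with control of the family-wise error at 5% for the efficacy endpoints under this hierarchy.

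If the sponsor prefers no gate, both documents should say that error is controlled within the secondary family only, and that secondary findings are exploratory when the primary is missed.

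The cost is a few sentences, with no new data, no patients and no loss of primary power. The real downside is that secondary efficacy results, including the separately sized mortality comparison, cannot be presented as confirmatory if time to intubation is not significant. Keeping three primaries with a Bonferroni split (0.0167 each) would instead cut time-to-intubation power to about 68% (Freedman, 60 events).
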